3.3 Parametric Analysis and Model Selection

• Parametric Survival Models:

- Candidate models include Gompertz, Weibull, exponential, log-logistic, lognormal, and Royston–Parmar flexible parametric models. Model fit will be assessed using the Akaike Information Criterion (AIC), Bayesian Information Criterion (BIC), and Cox–Snell residual plots.
- The model providing the best fit will be used to estimate hazard rates, survival probabilities, and restricted mean survival times.

• Hazard Deceleration (HD) Analysis:

- HD curves will be derived from the parametric hazard function, capturing changes in hazard rates over time.
- Inception points for anticoagulation resumption will be identified based on HD values falling below 5% of the initial hazard peak, indicating stabilization of HT risk.

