This analysis aims to evaluate the timing of anticoagulation resumption in MCA stroke patients treated with Cerebrolysin, stratified by hemorrhagic transformation (HT) risk. The primary focus is on determining Cerebrolysin's effect on the incidence and hazard of HT over time and establishing the optimal timing for anticoagulation resumption using advanced survival and hazard-based methods. Patients will be categorized into low-risk (HTI = 0) and high-risk (HTI > 0) groups based on the Hemorrhagic Transformation Index (HTI) scores, and outcomes will be analyzed for both symptomatic and any HT within 14 days.

2. Objectives and Endpoints

- **Primary Objective**: To evaluate the effect of Cerebrolysin on the timing of safe anticoagulation resumption in stroke patients with varying HT risk levels.
- Primary Endpoints:
 - Incidence of **any HT** and **symptomatic HT** over 14 days.
 - **Timing of Anticoagulation Resumption**: Defined by inception points based on hazard deceleration (HD) curves.

• Secondary Endpoints:

- \circ Survival probabilities for HT stratified by HT risk groups (HTI = 0 vs. HTI > 0).
- Hazard and risk reduction metrics, including hazard ratios (HR), absolute risk reduction (ARR), number needed to treat (NNT), and restricted mean survival time (RMST) differences for symptomatic and any HT.

3. Statistical Analysis

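### The Part III inception rule sets an undefined hazard-deceleration value against a fraction of a hazard; on its plain reading the cut-off depends on the time unit and marks no consistent level of remaining hazard

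*SAP*

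**What the plan says.** Part III, Section 2 (Objectives and Endpoints) lists the timing of anticoagulation resumption as a primary endpoint, "Defined by inception points based on hazard deceleration (HD) curves". The only operational definition is in Part III, Section 3.3. It says that "HD curves will be derived from the parametric hazard function, capturing changes in hazard rates over time" and places the inception point at "HD values falling below 5% of the initial hazard peak, indicating stabilization of HT risk".

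The hazard comes from whichever parametric model fits best: "Candidate models include Gompertz, Weibull, exponential, log-logistic, lognormal, and Royston–Parmar flexible parametric models".

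The section gives no formula for HD, no normalisation, and no time unit for the rule. Days enter Part III as the length of the follow-up window: "Incidence of any HT and symptomatic HT over 14 days". Section 5 of Part III expects the results to guide when anticoagulation is restarted, by risk stratum.

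**The concern.** A threshold rule needs the same kind of quantity on both sides. Here the left side describes how the hazard changes with time, and the right side is 5% of the hazard itself. If HD is the time derivative, the number 0.05 is not a pure proportion. It is a rate of 0.05 per time unit, and its meaning changes with the unit.

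This arises even for a steadily falling hazard with a finite peak. Nor is it only formal. The rule is said to show that HT risk has stabilised, so the inception point should correspond to some recognisable level of remaining hazard. If that level varies widely with the speed of decline, inception days from different arms or HTI strata are not comparable.

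**Working it through.** **Inputs.** From Section 3.3: HD as change in the hazard over time, read as HD(t) = −dh/dt; cut-off 0.05 × h_peak; Gompertz, lognormal and log-logistic among the candidate models. From Part III, Sections 1 and 2: a 14-day window. Assumed, because the SAP gives none: the decay rates g and the parameters of the other hazards. The SAP states no inception day, peak hazard or fitted parameter, so there is no figure of its own to reproduce.

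**Step 1: units, no data needed.** Record time with k units per day. Then h becomes h/k and dh/dt becomes (dh/dt)/k². The rule −dh/dt < 0.05 × h_peak becomes, in per-day terms,

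−dh/dt < 0.05 × k × h_peak.

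The effective cut-off scales with k.

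**Step 2: the rule in days.** Take h(t) = λ·exp(−g·t), with its peak λ at t = 0. The rule is g·exp(−g·t) < 0.05, so

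t* = ln(g/0.05)/g, or t* = 0 if g ≤ 0.05.

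The hazard left at t* is exp(−g·t*) = 0.05/g of the peak.

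| g per day (assumed) | t* in days | hazard left, % of peak |
|---|---|---|
| 0.05 or less | 0 | 100 |
| 0.06 | ln(1.2)/0.06 = 3.04 | 83.3 |
| 0.1 | ln(2)/0.1 = 6.93 | 50 |
| 0.2 | ln(4)/0.2 = 6.93 | 25 |
| 0.5 | ln(10)/0.5 = 4.61 | 10 |
| 1.0 | ln(20)/1.0 = 3.00 | 5 |

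Hazards falling at 0.1 and 0.2 per day get the same day with a twofold difference in the share of the peak remaining. Hazards falling at 0.06 and 1.0 per day both get about day 3, with 83% and 5% remaining.

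There is also a ceiling. t* is largest when ln(g/0.05) = 1, that is g = 0.05e, giving t* = 1/(0.05e) = 7.36 time units. Under a falling Gompertz hazard, no data could place the inception point later than 7.36 of whatever unit is used.

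**Step 3: the same hazards in other units, converted back to days.** For g = 0.5 per day, g is 0.0208 per hour (below 0.05, so day 0) and 3.5 per week (ln(70)/3.5 = 1.214 weeks = 8.50 days).

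| Hazard (assumed) | hours | days | weeks |
|---|---|---|---|
| Gompertz, g = 0.3/day | 0 | 5.97 | 12.46 |
| Gompertz, g = 0.5/day | 0 | 4.61 | 8.50 |
| Gompertz, g = 1.0/day | 0 | 3.00 | 4.94 |
| Lognormal, median 2 days, sigma 1 (peak day 1.24) | from the peak | 6.26 | 25.51 |
| Log-logistic, scale 3 days, shape 2 (peak day 3.0) | from the peak | 9.43 | 28.51 |

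The last two rows were solved numerically, as the time after the peak from which HD stays below the cut-off.

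**Step 4: other readings of HD.**
- *Change over a step s*, h(t) − h(t+s). The units now match, but the step is not stated. For Gompertz the hazard left is 0.05/(1 − exp(−g·s)). With s = 1 day this is 0.05/0.0952 = 52.5% at g = 0.1 and 0.05/0.6321 = 7.9% at g = 1.0, so the inconsistency remains.
- *Second derivative.* Still unit-dependent: 0, 1.96 and 14.93 days (hours, days, weeks) at g = 0.3 per day.
- *HD against 5% of its own peak.* Unit-free. For Gompertz t = ln(20)/g, for example 9.99 days at g = 0.3, against 5.97 under the rule as plainly read. This is shown only to demonstrate unit invariance and to show that the reading changes the answer.

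**The case against.** The strongest objection is that the derivative is inferred. The SAP prints no formula, and its loose wording could mean a day-to-day difference or HD relative to its own starting value. That is fair. The own-peak reading would remove the unit problem, and the step reading would replace it with an unstated step. But the text names the hazard's peak as the reference, and neither alternative is written. The openness is itself part of the fault, because the readings give different days from the same fitted curve.

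A reader might go further and infer that two analysts with the same data and model would report different days, one of them day 0. The document does not support that. Its follow-up window is in days, and hours and weeks are never named as analysis units. Two analysts who both took the derivative and worked in days would agree. The hours and weeks columns demonstrate the algebra and do not forecast what would happen.

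It is also true that the decay rates are invented, so the day figures measure no effect in this trial. Finally, the rule belongs to an analysis added in April 2024, and Part III's own limitations section asks for cautious interpretation and prospective validation. That limits the reach of the point but does not make the rule usable.

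**Conclusion.** The point stands in this form: HD has no formula, and on its plain reading the inception rule compares quantities of different dimension, so its cut-off depends on the time unit. That dependence is algebraic and needs no assumed data.

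In days the practical consequence is an arbitrary cut-off. Over assumed Gompertz decay rates of 0.1 to 1.0 per day, the hazard remaining at the inception point runs from 50% to 5% of its peak, and at 0.05 per day or slower the rule is met on day 0 with the hazard at its peak. The rule therefore does not reliably show the stabilisation it is said to indicate. These sizes rest on the derivative reading and on illustrative rates.

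The damage is confined to one Part III primary endpoint, the timing of resumption. The hazard ratios, ARR, NNT and RMST differences of Part III, and the HT comparison of the original study, do not use this rule. Because nothing else in the SAP defines that endpoint, it should be corrected before any inception day is relied on.

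**What to change.** In Part III, Section 3.3:

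1. Define HD by formula, including any step or normalisation.
2. State the time unit of the analysis.
3. Express the threshold in the same kind of quantity as HD, so that the result does not change with the time unit.
4. Re-run the inception calculation for each arm and HTI stratum under the corrected definition.

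The clinical team must reconcile the criterion and its threshold with the stated aim of showing that HT risk has stabilised. This review proposes neither a threshold nor a resumption time.

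The cost is one or two sentences in the SAP and a re-run from models already fitted. No new data are needed.

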3.5 Subgroup and Sensitivity Analyses

- Subgroup Analysis:
 - Separate analyses for low-risk (HTI = 0) and high-risk (HTI > 0) groups will examine Cerebrolysin's effects across HT risk strata.
- Sensitivity Analysis:
 - Parametric and semiparametric models will be compared using the Hausman specification test to ensure model consistency and robustness.

4. Software and Statistical Significance

- **Software**: Stata/SE v.17.0.
- **Significance Level**: α = 0.05 for primary and secondary analyses, with multiple hypothesis correction using the Romano-Wolf adjustment.

5. Interpretation and Reporting

- Clinical Implications:
 - Findings will inform optimal anticoagulation timing in stroke patients treated with Cerebrolysin, stratified by HT risk.
- Reporting:
 - Results will be reported with corresponding HRs, ARR, NNT, and RMST differences, stratified by HTI categories. Visualizations will include Kaplan–Meier curves, hazard plots, and survival curves for clarity.

6. Limitations

• This analysis relies on post hoc stratification, which may introduce selection bias. Results should be interpreted cautiously and validated in prospective studies.

This SAP outlines a robust framework for analyzing the impact of Cerebrolysin on HT incidence and anticoagulation timing in ischemic stroke patients, ensuring methodological rigor and clinical relevance.

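### The Part III anticoagulation-timing rule compares a change in hazard with a hazard level: its date depends on an unstated time unit, step and arm, and it detects a flat hazard rather than a low one

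*SAP*

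**What the plan says.** All of this is in Part III, the survival analysis added on 25 April 2024.

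- Section 2 (Objectives and Endpoints) sets the primary objective: "To evaluate the effect of Cerebrolysin on the timing of safe anticoagulation resumption in stroke patients with varying HT risk levels". Timing of resumption is a primary endpoint: "Defined by inception points based on hazard deceleration (HD) curves".
- Section 3.3 (Parametric Analysis and Model Selection) describes HD: "HD curves will be derived from the parametric hazard function, capturing changes in hazard rates over time". It then gives the rule: "Inception points for anticoagulation resumption will be identified based on HD values falling below 5% of the initial hazard peak", and reads a crossing as "indicating stabilization of HT risk".
- The hazard comes from whichever model fits best: "Candidate models include Gompertz, Weibull, exponential, log-logistic, lognormal, and Royston–Parmar flexible parametric models".
- Section 3.5 keeps the risk strata apart: "Separate analyses for low-risk (HTI = 0) and high-risk (HTI > 0) groups will examine" the treatment effect.
- Section 5 states the use: "Findings will inform optimal anticoagulation timing in stroke patients treated with Cerebrolysin, stratified by HT risk". Section 6 asks for cautious interpretation and prospective validation.

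Section 3.3 has no HD formula, time unit, time step or condition on the hazard level. It does name a reference, the initial hazard peak, but not the arm it comes from.

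**The concern.** A hazard is a rate per unit time, and its change over time is a different quantity. A rule that asks when the second is below 5% of the first needs a time unit or a step before it gives a date, and two analysts could report different days from the same fitted curve.

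The larger issue is what a crossing means. A small change says that waiting longer removes little further hazard. It does not say that the hazard is small. The stated objective is safe resumption, which is a question about how much risk remains.

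The question of whose peak is used also matters, because the objective is the effect of Cerebrolysin on this date.

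**Working it through.** **Inputs.** From the SAP: the 5% threshold and the candidate models (Part III, 3.3), the 14-day window (Part III, section 2), and 20% HT in controls (Part I, section 4). The SAP gives no decay rate and no inception date, so there is no plan figure to reproduce. All decay rates g below are assumptions.

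**Set-up.** Take a declining Gompertz hazard, h(t) = h0·exp(−g·t), with its own peak h0 as reference.

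- HD as derivative: g·h(t) < 0.05·h0 gives t = ln(20g)/g, with 0.05/g of the peak left.
- HD as difference over step s: h(t) − h(t+s) < 0.05·h0 gives t = ln(20·(1 − exp(−g·s)))/g, with 0.05/(1 − exp(−g·s)) of the peak left.

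h0 cancels, so these dates do not depend on HT incidence.

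**1. Flat is not low (time in days).**

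| g per day | Derivative: day, peak left | One-day step: day, peak left |
|---|---|---|
| 0.1 | ln 2/0.1 = 6.9, 50% | 6.4, 53% |
| 0.2 | ln 4/0.2 = 6.9, 25% | 6.4, 28% |
| 0.3 | ln 6/0.3 = 6.0, 17% | 5.5, 19% |
| 0.5 | ln 10/0.5 = 4.6, 10% | 4.1, 13% |
| 1.0 | ln 20/1.0 = 3.0, 5% | 2.5, 8% |

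The first two rows get the same date with a twofold difference in relative hazard. At 0.05/day the derivative is never above the threshold, although exp(−0.7) = 50% of the peak remains at day 14.

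To put this on a risk scale, choose h0 so that 20% have HT by day 14: h0·(1 − exp(−14g))/g = −ln 0.8 = 0.223. The cumulative hazard from the derivative date to day 14 is then h0·(0.05/g − exp(−14g))/g.

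- g = 0.1: h0 = 0.0296; 0.0296 × (0.500 − 0.247)/0.1 = 0.075, a 7.2% risk of HT still to come.
- g = 0.2: h0 = 0.0475; 0.0475 × (0.250 − 0.061)/0.2 = 0.045, or 4.4%.
- g = 0.5: h0 = 0.1117; 0.1117 × (0.100 − 0.001)/0.5 = 0.022, or 2.2%.

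**2. Time unit and step.** At g = 0.3/day the derivative rule gives day 6.0 in days. In hours, g = 0.3/24 = 0.0125, which is already below 0.05, so the rule is met at time 0. At g = 0.2/day, steps of half a day, one day and two days give days 3.2, 6.4 and 9.4.

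**3. Candidate models.** An exponential fit has HD = 0 throughout and meets the rule at time 0, whatever its hazard. A Weibull or log-logistic fit with shape below 1 has an infinite hazard at time 0, hence no finite peak. So does a Royston–Parmar fit on the log cumulative hazard scale with slope below 1 before the first knot. For a Weibull shape of 0.5, HD < 0.05·h(t0) gives t = (10·√t0)^(2/3). Reading the peak at t0 = 0.01, 1/24 or 1 day gives day 1.0, 1.6 or 4.6.

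**4. Whose peak.** A proportional effect multiplies HD and an own-arm peak by the same HR, which cancels, so both arms get the same date under any model. With the control-arm peak for both, the treated date is ln(20·g·HR)/g. At g = 0.3 and HR 0.5, control is day 6.0 and treated is ln 3/0.3 = day 3.7.

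**The case against.** The strongest reply is that stabilization is what section 3.3 says it measures, and that it is a coherent aim: resume when a further day of waiting removes little hazard. That stands as a clinical choice. It does not carry over to the objective in section 2 or the use in section 5, which speak of safe and optimal timing. If HD were scaled to its own peak, a Gompertz fit would give a hazard-level rule, since HD = g·h; but the text scales to the hazard peak.

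Four further points limit the concern.

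- The SAP counts in days, and in days the derivative and the one-day difference differ by only about half a day. Imaging is scheduled at days 1, 7 and 14, so that gap is finer than scheduled detection. The wider spread needs hours or another step, which the SAP neither suggests nor rules out.
- A reader might infer that no reference peak is given at all. That is too strong: the initial peak is named, and the separate stratum analyses make a stratum-specific peak the natural reading. The open choice is mainly own-arm against common.
- Hump-shaped fits can be made to show more hazard left at the crossing, but the parameters matter. A log-logistic with rate 0.5/day and shape 2 implies 1 − 1/(1 + 7²) = 98% HT by day 14, and a lognormal with mu 1 and sigma 1 implies 95%, against the planned 20% in controls. Such examples give no support here.
- The trouble with the exponential and infinite-hazard fits arises only if such a model is selected. Under a truly constant hazard no rule of this kind gives a useful date.

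**Conclusion.** The concern holds for this one endpoint. As written, the rule does not fix a unique date, and the date it gives does not bound the hazard that remains. Dependence on unit, step and arm follows from the rule itself. The sizes rest on assumed decay rates: the same day 6.9 can leave 50% or 25% of the peak, while at 0.5/day or faster the remainder is 10% or less in day units.

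A reader might go further and infer that trial patients were put at risk, or that the HT findings are unreliable. The document supports neither. Part III is a secondary analysis, nothing in it says the rule governs any patient's care, and HT incidence, hazard ratios, ARR, NNT and RMST do not use HD. Nor can one say that the reported date is wrong, since the fitted hazard is not given. Severity is minor to moderate.

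**What to change.** **Section 3.3.** Define the inception point as the first time after the peak at which the fitted hazard, in days, falls below a prespecified fraction (for example 5%, chosen with the clinical team) of the control-arm peak within the same HTI stratum, used for both arms. Take the peak over days 1 to 14 for every candidate model, and look for inception only from day 1, when the first follow-up imaging is scheduled. This deals with infinite initial hazards in one uniform way. Report *not reached by day 14* where that applies. Beside each date, report the hazard and the remaining cumulative HT risk to day 14, because a relative threshold alone does not establish safety.

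If HD is kept as a measure of stabilization, give its formula in days, scale it to the peak HD of the same curve, and show the hazard left beside it.

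**Sections 1, 2 and 5.** Describe the result as the time course of HT hazard, not as safe or optimal timing.

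**Example** (assumed g = 0.3/day, 5%): control reaches the point at 1 + ln 20/0.3 = day 11.0, and a treated arm with HR 0.5 at 1 + ln 10/0.3 = day 8.7.

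**Cost.** Wording and recomputation from the fitted models, with no new data. Some fits will give no date: a Gompertz decay below ln 20/14 = 0.21/day with the peak at day 0, or below ln 20/13 = 0.23/day with the peak at day 1. The timing claim becomes weaker.

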3.2 Survival Analysis

• Nonparametric Analysis:

- Kaplan–Meier survival curves will be generated for symptomatic and any HT, stratified by HT risk group and treatment arm. Log-rank tests will compare survival distributions.
- The proportional hazard (PH) assumption will be tested using graphical diagnostics and statistical methods, with alternative combined permutation tests if the assumption is violated.

• Semiparametric Analysis:

- Cox proportional hazards models will estimate hazard ratios (HRs) for symptomatic and any HT, adjusting for HTI category and treatment group.
- If the PH assumption is violated, time-dependent Cox models with time-varying covariates will be employed.

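### The SAP does not say whose peak sets the 5% inception threshold; if each curve is judged against its own peak, a proportional fall in HT hazard cannot move the Part III timing endpoint.

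*SAP*

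**What the plan says.** SAP Part III, section 2 gives the primary objective as "To evaluate the effect of Cerebrolysin on the timing of safe anticoagulation resumption in stroke patients with varying HT risk levels". One of its primary endpoints is the timing of anticoagulation resumption, "Defined by inception points based on hazard deceleration (HD) curves".

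Section 3.3 supplies the operational rule. On the curves it says: "HD curves will be derived from the parametric hazard function, capturing changes in hazard rates over time". The inception points are then to be "identified based on HD values falling below 5% of the initial hazard peak, indicating stabilization of HT risk". No formula for HD follows. The reference peak is not assigned to an arm, a stratum, the control group or the pooled data. Part III sets no absolute hazard or residual-risk limit.

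The hazard comes from the best-fitting member of a list: "Candidate models include Gompertz, Weibull, exponential, log-logistic, lognormal, and Royston–Parmar flexible parametric models". In section 3.2, "Cox proportional hazards models will estimate hazard ratios (HRs) for symptomatic and any HT", adjusted for HTI category and treatment group. Section 3.5 adds: "Separate analyses for low-risk (HTI = 0) and high-risk (HTI > 0) groups will examine Cerebrolysin's effects across HT risk strata".

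**The concern.** The threshold is a fraction of a peak hazard. If that peak belongs to the curve being judged, the rule is relative: it measures how fast a hazard declines from its own maximum and ignores how high the hazard is. A treatment that lowers the HT hazard by the same factor at every time lowers the curve and its threshold together, so the crossing day stays put. Yet that is the effect a Cox hazard ratio summarises, and Part III asks whether the drug changes the timing.

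Two misreadings are at stake. Equal days in the two arms could be taken as no drug effect on timing. Equal days in two risk groups could be taken as equal safety, since section 3.3 equates the crossing with stabilised HT risk and section 5 says the findings will inform anticoagulation timing by HT risk.

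**Working it through.** The SAP states no inception day and no expected shift, so there is no figure of its own to reproduce. The check is algebra followed by illustration.

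**Inputs from the SAP**
- Threshold: 5% of the peak hazard (Part III, section 3.3).
- Window: 14 days (Part III, sections 1 and 2).
- Planning effect: 20% HT in controls and OR 0.5 (Part I, section 4). The control odds are 0.20/0.80 = 0.25; halved they are 0.125; the Cerebrolysin risk is 0.125/1.125 = 11.1%.
- Equivalent hazard ratio over 14 days: ln(1 − 0.1111)/ln(1 − 0.20) = 0.1178/0.2231 = 0.528.

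**Assumed inputs**
- Group risks of 5% and 30% to span low and high HT risk.
- All hazard shapes.
- HD(t) = −h′(t), with time in days.

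**Step 1: algebra.** Let h₁(t) = c·h₀(t). Then −h₁′(t) = c·(−h₀′(t)) and peak₁ = c·peak₀. The condition −h₁′(t) < 0.05·peak₁ reduces to −h₀′(t) < 0.05·peak₀, and c cancels. It also cancels if HD is the hazard level compared with its peak, or the slope compared with its own peak slope. The missing HD formula therefore does not affect this result.

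**Step 2: Gompertz, h(t) = λ·exp(−g·t).** The peak is λ, and HD is g·λ·exp(−g·t). The own-peak crossing is at t* = ln(20g)/g, which contains no λ. With g = 0.5, t* = ln(10)/0.5 = **4.61 days** at every risk level.

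The share of the 14-day cumulative hazard still to come at t* is (e^(−g·t*) − e^(−14g))/(1 − e^(−14g)) = (0.1000 − 0.0009)/(1 − 0.0009) = 0.0992. The remaining risk is 1 − (1 − p)^0.0992, where p is the 14-day risk:

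| 14-day HT risk | Inception day (own peak) | HT risk from that day to day 14 |
|---|---|---|
| 5% | 4.61 | 0.5% |
| 11.1% | 4.61 | 1.2% |
| 20% | 4.61 | 2.2% |
| 30% | 4.61 | 3.5% |

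One day thus stands for about a 7-fold range of remaining risk (3.48/0.51 = 6.8).

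**Step 3: common reference, for contrast.** Judged against 5% of the control peak, the Cerebrolysin curve crosses at ln(20g × 0.528)/g = ln(5.28)/0.5 = **3.33 days**, against 4.61 in control. The shift is −ln(0.528)/g = 1.28 days. With g = 0.25 or 1.0 it is 2.56 or 0.64 days. The own-peak shift is zero in all three cases.

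**Step 4: effect on the early hazard only.** Take h(t) = A·e^(−t) + 0.01·e^(−t/6), with peak A + 0.01 and HD = A·e^(−t) + (0.01/6)·e^(−t/6).
- A = 0.04: the threshold is 0.0025 and the crossing is at day 3.26. The 14-day cumulative hazard is 0.04 + 0.06·(1 − e^(−14/6)) = 0.0942, a risk of 9.0%.
- A = 0.01: the threshold is 0.0010 and the crossing is at day 4.12. The cumulative hazard is 0.0642, a risk of 6.2%.

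The second hazard is lower at every time, yet its day is later because its own peak, and so its threshold, fell.

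**Step 5: different shapes.** With own-peak Gompertz curves of decay 0.5 and 0.4 per day, the days are 4.61 and ln(8)/0.4 = 5.20. The days now differ, but still only through g. The level λ plays no part.

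**The case against.** The strongest reply is that the SAP never says own peak. It says only that there is an initial hazard peak, and with a control or pooled peak the endpoint does respond, as step 3 shows. This stands: own peak is an inference. It is the natural one, because HD is derived from a fitted hazard and the HTI groups are analysed separately. Under the other reading the reference curve is still undefined, and the same clarification is needed.

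A reader might infer that the low- and high-risk HTI groups must receive the same day. The SAP does not support that. Equality needs proportional hazards with a common shape. Section 3.2 tests proportionality and plans for its failure, section 3.3 admits non-proportional models, and section 3.5 analyses the HTI groups separately. The Cox model does not bind the inception point, which comes from the chosen parametric model. Differing shapes give differing days, but these still reflect the form of the decline and not the level of risk.

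A reader might also infer that an effective drug will generally look harmful on timing. Step 4 shows only that it can, with freely chosen parameters. Under lognormal hazards at the planning effect, with the same HD definition, the direction depends on the assumed sigma. The control and Cerebrolysin days are 2.83 and 3.55 at sigma 3, and 4.34 and 4.24 at sigma 2.5; at sigma 2 there is no crossing in either arm. No general direction can be claimed.

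Lastly, Part III would not overlook an effective drug. HT incidence is also a primary endpoint, and HR, ARR, NNT and RMST are reported. Section 6 asks for cautious interpretation and prospective validation. This limits the damage to the timing endpoint but does not repair it, and section 6 does not mention the problem.

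**Conclusion.** The point holds in conditional form. The HD formula and the reference peak are undefined. If the peak is each curve's own, the timing endpoint is insensitive to any proportional change in HT hazard: the shift is exactly 0 days whatever the size of the effect, and for each of the three readings of HD considered. That conflicts with the Part III primary objective. HTI groups share a day only if their hazards are proportional with a common shape.

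The zero shift needs no numerical assumption beyond own-peak scaling, proportionality and a hazard with a finite peak that crosses the threshold. The size of what it hides does rest on assumptions. With Gompertz decay of 0.5 per day and slope-based HD, one day covers remaining risks from 0.5% to 3.5%, and a control-peak reference would have shown a 1.28-day difference at the planning effect (2.56 to 0.64 days for decay of 0.25 to 1.0). These days are illustrations and do not predict the trial's result.

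**What to change.** In SAP Part III, sections 2 and 3.3:

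1. Give the HD formula and its time unit, and name the curve whose peak is the reference.
2. Reconcile the rule with the primary objective. Use either one reference hazard common to all arms and HTI strata, or an absolute model-based quantity such as modelled HT risk from a given day to day 14.
3. Report modelled hazard and remaining HT risk to day 14 at each inception day, by arm and HTI stratum.
4. If an own-peak result is kept, state beside it that equal days show neither equal safety nor absence of a drug effect.

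The acceptable level of hazard or remaining risk is a clinical decision for the sponsor, and none is proposed here. The cost is SAP wording and a re-run of existing model output. No new data are needed.
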